3.2 Eligibility criteria

3.2.1 INCLUSION CRITERIA

- 1. The CYP has an accepted referral to CYPGS, or has already attended an appointment at a CYPGS.
- 2. The CYP is awaiting or has received their first appointment with the service at the time of completing baseline measures.
- 3. Valid assent/consent has been obtained:
 - a) For CYP under the age of 16 at recruitment providing self-reports:
 - i. Parent/legal guardian gives consent for them to participate AND
 - ii. CYP gives assent to participate.CYP is deemed to have capacity to consent by their clinician and gives consent to participate.
 - b) For CYP 16 years and above providing self-report information:
 - i. CYP gives consent to participate. OR
 - ii. Personal Consultee gives consent for the CYP to participate if the CYP lacks capacity to consent.
 - c) For parent-reported measures for CYP under the age of 16 at recruitment: Parent/legal guardian consents to their own participation to provide parent-reported measures.
 - d) For parent-reported measures for CYP 16 years and over at recruitment: Parent/legal guardian consents to their own participation to provide parent-reported measures and CYP consents to parent/legal guardian completing measures.

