3.3 Informed consent

All CYP and their parents/carers/legal guardians attending the CYPGS will receive the participant information sheet (PIS) about the study and will be invited to provide assent/consent electronically via the Medrio eConsent module (see section 5.1.2).

Assent/consent from CYP and parents/legal guardians will be considered semi-independent. That is, a parent may choose to provide information about their CYP, even if that CYP declines to participate by providing self-reports. For CYP under age 16 years, parental consent for them to participate is generally required, but can be given even if the parent decides not to participate themselves. CYP 16 years and over will be asked whether they consent to their parent or another trusted adult completing informant versions of questionnaires.

For CYP who turn 16 years during the study period, consent will be taken prior to or at the next assessment point. Informed assent/consent will be obtained from CYP and parents/legal guardians at baseline before any assessment measures are completed. Assent/consent will be documented electronically, and participants will be assured that their decision to participate (or not) will not affect their access to care or future care pathways. This includes endocrine care and involvement in the randomised controlled trial evaluating gonadotropin releasing hormone analogues (GnRHa), PATHWAYS TRIAL.

Parents/legal guardians of CYP <16 and YP 16 years and older will be contacted by the CYPGS to obtain consent and provide their email addresses for PATHWAYS HORIZON researchers to contact them about the study. The PIS will then be sent to participants with other information about their first appointment. Given the relatively low risk nature of this questionnaire study, after receiving the PIS, participants will have the following options:

- 1. To assent/consent electronically.
- 2. To request that a researcher gets in touch to tell them more about the study.
- 3. To delay the decision until after their first appointment in the CYPGS (and be contacted then to answer any questions).
- 4. To decline participation.

The process of contacting and obtaining assent/consent is as follows:

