- 6. Informed consent from one parent/legal guardian for CYP under 16 years and consent from CYP 16 years and older will be obtained prior to completion of baseline measures. This consent will be taken separately for CYP self-report and parental report. There is no upper time limit for CYP and their parents/carers/legal guardians to consider participation and they will be encouraged to ask any further questions about the study, including referring to the study website which will develop a section specifically for study participants.
- 7. It is possible there will be rare instances in which the CYP wishes to participate but the parent/legal guardian does not provide informed consent. In such instances, consideration of the CYP's ability to provide informed consent will be delayed until they have been assessed in the CYPGS. The clinical keyworker or their clinical delegate will be requested to assess the CYP's ability to provide informed consent and to consider any disadvantages for their clinical care if they participate against parent support (e.g., family disharmony). The clinician's opinion regarding the CYP's ability to provide informed consent will be recorded in the clinical notes. If they deem the CYP able to provide consent, they will provide an additional signature on the

consent form. Professionals conducting an assessment will have access to training and consultation from a Consultant Paediatrician or Psychiatrist based in the CYPGS.

Study participation will routinely be recorded in the participant's medical record unless a risk is identified. In such cases, the local risk protocol will be followed, which may lead to CYPGS triggering safeguarding or other referrals as necessary at the local site.

Families with CYP unable to complete the baseline assessments, e.g., due to significant intellectual disability, will still be invited to participate in completing parent-reported and clinician-recorded measures. Families with parents/carers/legal guardians who are unable to complete study questionnaires will still be allowed to participate in the study provided they can provide informed written consent, for the CYP (if less than 16 years) to take part in the study.

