4.1.1 Enrolment visit

Participants may enrol electronically or in person, providing e-consent. Enrolment for CYP-reported measures is considered complete when there is (1) valid consent from CYP 16 years or older (2) valid consent from a parent/legal guardian of CYP under 16 years and CYP assent or (3) valid consent from a CYP under 16 years where deemed to have capacity to consent by their clinician or 4) valid consent from a Personal Consultee where CYP 16 years or older lacks capacity to consent.

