4.4.3 Annual follow-up timepoints only

4.4.3.1 Annual health update

A questionnaire was designed to assess the CYP's current height and weight, current prescribed medications and diagnoses including neurodevelopmental, mental health and physical health, received in the past year. The questionnaire also assesses the number of GP appointments, planned surgeries or procedures, A&E attendances, or other unplanned admissions in the past year. The reasons for the GP appointments and A&E attendances will be elicited. The length of hospital admission for planned surgeries or procedures and admissions following an A&E attendance will also be measured. At follow-up, parents/carers/legal guardians of CYP under 16 will be sent this questionnaire and asked to complete it with their CYP. Self-report questionnaires will only be obtained from young people aged 16 and above. Duration: 6 minutes.

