6. ADVERSE EVENT MANAGEMENT AND REPORTING

Adverse events (AEs) will be recorded based on specific items endorsed by either the CYP or parent/ caregiver in the questionnaires as outlined in section 4.5.1 and the PATHWAYS HORIZON distress protocol, including the ASQ, Annual Health Update and RCADS-25.

Any SAEs occurring to research participants will be reported to the main REC (the REC that gave favourable opinion of the study) within 15 days of the Chief Investigator becoming aware of the event, or the Deputy Chief Investigator in the Chief Investigator's absence.

The up to date SAE report form for non-CTIMPs available from the HRA website will be used for this indication.

Based on the data that are being collected AEs will include:

- 1. Depression or anxiety scores with a T score ≥80 on annual questionnaires when they previously were not (RCADS)
- 2. Suicidal thoughts and behaviours (ASQ)
- 3. Unplanned A&E attendances for mental health (Annual Health Update)
- 4. Unplanned hospital admission for any reason other than mental health (Annual Health Update)

SAEs will be recorded when:

1. Unplanned hospital admission for mental health (Annual Health Update)

Standard safeguarding procedures will be followed if a CYP or parent endorses the questionnaire item relating to an unplanned hospital admission for mental health (SAE). All PATHWAYS researchers who have access to the research database or direct contact with research participants will have level 3 safeguarding training. The PATHWAYS research team also consists of two senior clinical academics with longstanding experience of managing safeguarding concerns, who will be available daily to advise on any safeguarding concerns.

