Annex 1 – Consent Flowchart

Annex 2 – Individual Schedule of Events

Table 2: Schedule of Events for information collected from CYP

Event/Form	Domain, information source (see legend)	Baseline	Month 12	Month 24	Annual Follow Up	Estimated completion time (minutes)
Informed consent/ assent	SQ (1)	X				10
Quality of Life (KIDSCREEN-52)	SQ, PQ (2)	X	X	X	X	7
Annual health update (CYP 16+ only)	SQ, PQ (6) (7)		X	X	X	6
Gender Identity Questionnaire	SQ, (3)	X	X	X	X	1
Social Transition Questionnaire	SQ (3)	X	X	X	X	1
Anxiety and depression symptoms (RCADS-25)	SQ, PQ (4) (7)	X	X	X	X	5
Suicide/ Self Harm (ASQ)	SQ, PQ (4) (7)	X	X	X	X	1
Gender dysphoria (UGDS-GS)	SQ (3) (7)	X	X	X	X	3
Body image/ dysphoria (BIS-GS)	SQ (3)	X	X	X	X	3
Emotional Dysregulation (DERS-18)	SQ, PQ (4)	X	X	X	X	3
Sexual Attraction Questionnaire (CYP 12+ only)	SQ (3)	X	X	X	X	1
Romantic Relations (ALSPAC measure; CYP 12+ only)	SQ (3)	X	X	X	X	5
Parental support (PAGES-Y)	SQ (4)	X	X	X	X	3
Trauma (APCTSS)	SQ, PQ (4)	X	X	X	X	2
Emotional & Behavioural Problems (CBCL, YSR)	SQ, PQ (4)	X	X	X	X	15
Eating Problems (SCOFF)	SQ, PQ (4)	X	X	X	X	1

LEGEND

Domains:

1=protocol adherence; 2= personal priorities and quality of life; 3= gender; 4=mental health; 5= neurodevelopmental difference; 6=physical health; 7=adverse events **Information source:**

R=researcher-completed; SQ=self-reported questionnaire; PQ=parent-reported questionnaire; D=direct observation/examination

^{*} If a participant turns 16 during the study, consent must be sought

Table 3: Schedule of Events for information collected from parents/carers/legal guardians

Event/Form	Domain, information source (see legend)	Baseline	Month 12	Month 24	Annual Follow Up	Estimated completion time (minutes)
Informed consent/ assent	PQ (1)	X				10
ADHD (SNAP-IV)	PQ (5)	X				3
Autism (SCQ)	PQ (5)	X				5
Parental 'About yourself' Questionnaire	PQ(3)	X				1
Gender Identity Questionnaire	SQ, PQ**	X				
Quality of Life (KIDSCREEN-52)	SQ, PQ (2)	X	X	X	X	7
Annual health update (Parents of CYP under 16 only)	SQ, PQ (6) (7)		X	X	X	6
Anxiety and depression symptoms (RCADS-25)	SQ, PQ (4) (7)	X	X	X	X	5
Suicide/ Self Harm (ASQ)	SQ, PQ (4) (7)	X	X	X	X	1
Emotional Dysregulation (DERS-P)	SQ, PQ (4)	X	X	X	X	3
Parental Support (PAGES-P)	SQ, PQ (4)	X	X	X	X	3
Trauma (APCTSS)	SQ, PQ (4)	X	X	X	X	2
Emotional & Behavioural Problems (CBCL, YSR)	SQ, PQ (4) (7)	X	X	X	X	15
Eating Problems (SCOFF)	SQ, PQ (4)	X	X	X	X	1

LEGEND

Domains:

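### The Annual Health Update goes to a respondent chosen by age alone, so some validly enrolled participants have no eligible respondent for hospital admissions or for the study's only SAE category

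*Protocol*

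**What the plan says.** Section 4.4.3.1 describes the Annual Health Update as the yearly follow-up form on height, weight, medication, new diagnoses, GP contacts, A&E visits and admissions. Parents of under-16s receive it and complete it with the young person. For the rest, "Self-report questionnaires will only be obtained from young people aged 16 and above". Annex 2 repeats the split: the row in Table 2 is limited to those aged 16 and over, and the row in Table 3 reads "Annual health update (Parents of CYP under 16 only").

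The enrolment rules are wider than that split:

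- Section 3.3 says that, under 16, "parental consent for them to participate is generally required, but can be given even if the parent decides not to participate themselves".
- Section 3.2.1 admits an under-16 when the "CYP is deemed to have capacity to consent by their clinician and gives consent to participate", and section 4.1.1 counts this as complete enrolment: "valid consent from a CYP under 16 years where deemed to have capacity to consent by their clinician".
- Section 3.3 states that families whose child cannot complete the assessments "will still be invited to participate in completing parent-reported and clinician-recorded measures". No age limit is given. The same section lets a parent report when the young person declines self-report, and section 4.6.1 lets a parent continue after the young person withdraws, if the young person agrees.

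Section 6 names the form as the source of the single SAE category: "Unplanned hospital admission for mental health (Annual Health Update"). Section 8.2 lists hospitalisation as a binary secondary outcome.

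**The concern.** The respondent rule uses age, whereas the consent rules let the young person and the parent take part semi-independently. Where the two do not line up, the form has no one who can validly answer it, even though another consented informant, or the young person, is in the study and could.

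The Annual Health Update is the planned source for mental-health A&E attendances, other unplanned admissions and mental-health admissions. The last of these is the only SAE, and it starts the notice to the clinician or GP (section 4.5.1), the report to the REC and the safeguarding steps (section 6). The form also supplies follow-up height, weight and diagnoses. If the rule is followed exactly, these data are lost for some participants because of how the form is assigned, not because anyone declined to give them.

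**Working it through.** No sample-size, power or error-rate figure is involved. The check sets the enrolment routes against the respondent rule.

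| Enrolment route | Where | Respondent under 4.4.3.1 | Available? |
|---|---|---|---|
| Under 16, parent takes part | 3.2.1 | Parent | Yes |
| Under 16, parent consents for the child but does not take part | 3.3 | Parent | No, unless another adult consents to report |
| Under 16, enrolled on own consent | 3.2.1, 3.3, 4.1.1 | Parent | No, unless another adult consents to report |
| 16 or over, able and willing to self-report, with or without help | 3.2.1, 3.4.2 | Young person | Yes |
| 16 or over, cannot answer even with support, parent reports | 3.2.1, 3.3 | Young person | No |
| 16 or over, declines or withdraws from self-report, parent reports | 3.3, 4.6.1 | Young person | No |

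The uncovered rows form two groups: (a) under-16s with no consenting adult informant, and (b) those aged 16 or over who take part only through parent report.

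**What is lost.** Section 6 lists 4 AE categories and 1 SAE category, so 4 + 1 = 5. One AE comes from the RCADS and one from the ASQ. The other two AEs and the SAE come from the Annual Health Update: 2 + 1 = 3 of 5. The ASQ and RCADS have self-report and parent versions with no age split, so those two categories stay covered.

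**Other planned sources.** Medical history is taken at baseline only (Table 1). The status form records whether the participant remains in the service or study (sections 4.1.3 and 4.4.3.2). Data linkage is optional and belongs to longer-term follow-up (section 2). None replaces the form at an annual wave.

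**How long the gap lasts.** Group (a) is uncovered at each annual wave before the 16th birthday and moves to self-report afterwards. A member of group (b) who joined under 16 with a participating parent is covered until 16 and uncovered from then on.

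**How many.** The protocol gives no count for either group. For scale only: 1% of 3600 = 0.01 × 3600 = 36 participants.

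**Internal conflict.** Section 6 says that AEs are recorded from items endorsed by either the young person or the parent, and starts safeguarding when either endorses the admission item. Table 1 codes the form as both self- and parent-reported (SQ, PQ). Section 4.4.3.1 and the row labels in Tables 2 and 3 name one respondent by age. These cannot all be followed as written.

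**The case against.** The best defence is that the protocol already narrows the gap. Section 3.4.2 offers face-to-face, video or telephone completion and interpreters, so parents who only need help, and young people of 16 or over who can answer with help, are covered. Section 2 and section 4.6.2 allow another parent or carer to step in as informant. Section 3.3 calls enrolment on own consent against the parent's position rare. All of this stands, and it is why the two groups are drawn as tightly as they are. Support helps an informant to answer, however. It does not create one where no adult has agreed to report or where the young person cannot respond.

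Three stronger readings are tempting and should not be made:

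- A reader might infer that the form would be sent to a parent who has not consented. That is unlikely. Section 3.2.1(c) requires the parent's own consent for parent-reported measures, section 4.2.3 sets up ePRO access after consent, and section 5.1.3 bars ePRO entry without a signed form.
- A reader might infer that these participants would be counted as having had no event. Nothing in the protocol says that an absent form means no event, and section 8.8 addresses missing outcomes.
- A reader might infer that hospitalisation rates or DMC tables are biased in a known direction. No direction or size can be derived from the document. Section 5.5 already says that AE collection here is less comprehensive than in an RCT and that the DMC will be told so.

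It is also fair to say that the primary outcome, self-reported KIDSCREEN-10, does not depend on this form, and that chance disclosure could bring an admission to light (section 7.2.1). Chance disclosure is not a planned source.

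**Conclusion.** The concern holds as a structural gap. The age-only rule leaves two groups of validly enrolled participants without an eligible respondent for the Annual Health Update. While the gap lasts, 3 of 5 AE/SAE categories, including the only SAE, and the hospitalisation outcome have no planned source for them. The passages in section 4.4.3.1, section 6 and Tables 1 to 3 also need to be reconciled.

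The size is unknown and may be small. No percentage in the protocol supports an estimate, and the 36 participants per 1% is scale, not a forecast. A reader might also conclude that these participants are uncovered throughout follow-up. That does not hold for those who turn 16 and begin to self-report, nor for those whose parent answered until they reached 16.

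This is a should-fix point. It concerns safety and hospitalisation data in a cohort of young people, but only for an uncounted minority, and it leaves the primary outcome untouched. The conclusion assumes that the form is issued exactly as section 4.4.3.1 and Annex 2 describe.

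**What to change.** In section 4.4.3.1 and Tables 1 to 3, assign the Annual Health Update to the consented informant, with age only as the default:

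- under 16 with no consenting adult informant: self-report by the young person with researcher support, using the modes in section 3.4.2;
- 16 or over and not self-reporting: the parent version, sent to the consented parent.

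Bring the either-informant wording in section 6 into line with the new rule. Report hospitalisation and AE/SAE counts over participants with a completed form, so that anyone still without a respondent appears as not assessed.

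The cost is a short amendment and a changed ePRO assignment rule; the form is already planned for both kinds of respondent. The downside is that some under-16s may report admissions less accurately than a parent would. An early change is better, because a missed annual wave can be recovered only from later recall.

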4.4.3.2 Status Form

At each follow up timepoint, a status form is completed to document the participants' status in the study.

4.5 Safety data

4.5.1 Adverse events

The measures included at each assessment point (domain 7 – adverse events) will assess several adverse events (AE) experienced by the CYP since the last assessment. For this study, these will include suicidal thoughts and behaviour (captured by the ASQ), a marked increase in the severity of anxiety or depression symptoms (captured by the RCADS), A&E attendances due to mental health, and any unplanned hospital admissions (captured by the Annual Health Update). Mental distress requiring unplanned hospital admission (captured by the annual health update as any mental health related A&E admission) will be recorded as a serious adverse event (SAE) and will be reported to the CYP's lead clinician or care coordinator at the CYPGS, or their GP. The total duration of hospital admission will be recorded.

4.6 *Ongoing*

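### Section 4.5.1 captures the study's only SAE through A&E admissions, which is narrower than the section 6 definition, so a mental-health admission that bypasses A&E may not be identified as an SAE

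*Protocol*

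**What the plan says.** Four parts of the protocol bear on this.

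- **Section 6 (adverse event management and reporting)** lists a single SAE: "Unplanned hospital admission for mental health (Annual Health Update"). The matching adverse event (AE) is "Unplanned hospital admission for any reason other than mental health (Annual Health Update"). Neither depends on how the young person reached hospital. SAEs go to the main Research Ethics Committee (REC) within 15 days of the Chief Investigator, or the deputy in their absence, becoming aware of them.
- **Section 4.5.1 (adverse events)** makes mental distress that leads to unplanned admission an SAE and adds, in brackets, that it is "captured by the annual health update as any mental health related A&E admission". Its list of AEs includes "any unplanned hospital admissions (captured by the Annual Health Update") and does not take out admissions for mental health. It ends: "The total duration of hospital admission will be recorded".
- **Section 4.4.3.1 (annual health update)** describes the form that supplies these data. It counts A&E attendances and, separately, other unplanned admissions in the past year. On reasons it says: "The reasons for the GP appointments and A&E attendances will be elicited". On duration it says: "The length of hospital admission for planned surgeries or procedures and admissions following an A&E attendance will also be measured".
- **Sections 5.5 and 9.3** send AE and SAE data to the DMC, initially once a year. The data are for information, and serve as context for interpreting the PATHWAYS Trial.

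**The concern.** The definition of the SAE and the rule for finding it do not cover the same events. Section 6 covers every unplanned mental-health admission; the bracket in section 4.5.1 covers only those made through A&E. An admission arranged directly meets the definition but not the capture rule.

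SAE status is what triggers the REC report and entry in the SAE data seen by the DMC. If staff work from the section 4.5.1 wording, whether an admission is reported could depend on the route into hospital rather than on what happened to the young person. Section 5.5 warns the DMC that events are collected less comprehensively than in a randomised trial, but it does not say that the SAE count may depend on route.

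**Working it through.** No arithmetic applies; the check is a comparison of the sections. Take two unplanned admissions for mental health, one through A&E and one direct.

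| Question | Through A&E | Not through A&E |
|---|---|---|
| SAE under the section 6 definition? | Yes | Yes |
| Within the section 6 AE for admissions? | No, mental health is excluded | No, mental health is excluded |
| SAE under the main clause of section 4.5.1? | Yes | Yes |
| Met by the capture rule in the section 4.5.1 bracket? | Yes | No |
| Within the section 4.5.1 AE wording on unplanned admissions? | Yes | Yes |
| Counted on the form described in section 4.4.3.1? | Yes | Yes, as another unplanned admission |
| Reason described as collected? | Yes, for the A&E attendance | No |
| Length of stay described as collected? | Yes | No |

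Four steps follow from the table.

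1. **The definition is consistent.** Section 6 and the main clause of section 4.5.1 agree that both admissions are SAEs.
2. **The capture rule is narrower.** Only the admission through A&E satisfies it. The bracket is hard to read as shorthand for any unplanned admission, because section 4.4.3.1 itself separates A&E attendances from other unplanned admissions. The protocol recognises the category that the bracket leaves out.
3. **The form as described does not close the gap.** It would show that a direct admission took place, but with no reason attached it could not be told apart from an admission for, say, an injury.
4. **The duration gap comes from section 4.4.3.1.** Section 4.5.1 promises total duration without restriction. Section 4.4.3.1 describes length of stay only for planned procedures and for admissions that follow an A&E attendance.

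The revision history says that adverse event collection in sections 4.5.1 and 6 was clarified in version 1.1. The two sections were presumably meant to agree.

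**The case against.** A reader might go further and infer that the protocol grades a direct mental-health admission as an AE and not as an SAE. The documents do not support that. Section 6 excludes mental-health admissions from the AE and makes them the SAE. The main clause of section 4.5.1 does the same with no limit on route, and the A&E phrase is a note on capture, not a grading rule. Listing unplanned admissions generally among the AEs does not downgrade the subset that the next sentence makes serious.

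Nor does section 6 clearly hand precedence to section 4.5.1. Its cross-reference, "in the questionnaires as outlined in section 4.5.1 and the PATHWAYS HORIZON distress protocol", concerns how AEs are recorded and names a second document as well. SAEs have their own rule in section 6.

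The strongest point on the other side is that the form and the distress protocol are not shown. Section 6 refers to a questionnaire item on unplanned admission for mental health, labels it as the SAE, and does not mention A&E. Section 4.4.3.1 is a prose summary and may be incomplete. The form may therefore already ask the right question.

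The stakes are also limited. Section 7.2.1 promises that the clinician is told of any disclosed distress requiring admission, whatever the route. The DMC receives these data for information, not to make recommendations, and is told that collection is less comprehensive. No outcome in section 8.2 is claimed to be affected.

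All of this stands, and it sets the size of the point. It does not remove it. If the form asks by any route, sections 4.4.3.1 and 4.5.1 misdescribe it. If it does not, the SAE definition cannot be applied to direct admissions. The safeguard in section 7.2.1 covers neither the REC report nor the SAE data.

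**Conclusion.** The point holds as a mismatch between definition and capture. On the collection described, an unplanned mental-health admission that bypasses A&E may not be identified as an SAE. It may then miss the 15-day REC report and the SAE data given to the DMC, and its duration is not among the items described.

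The size is unknown. It lies between zero, if the form already asks by any route, and every mental-health admission made outside A&E. The protocol gives no admission rate and no share of admissions that bypass A&E, so no figure is offered.

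The conclusion rests on two assumptions: that the bracket in section 4.5.1 means what it says, and that section 4.4.3.1 describes the form fully. If the second fails, what remains is a correction of wording. It should still be made, because a stated rule for the study's only SAE would miss events if it were followed.

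**What to change.** - **Section 4.5.1:** replace the bracketed A&E wording with *any unplanned admission for mental health, by any route*. Limit the AE for admissions to reasons other than mental health. Both changes match section 6.
- **Section 4.4.3.1, and the form if it does not already do so:** collect the main reason and the length of stay for every unplanned admission.

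If the form already asks by any route, the cost is a wording change in two sections. If not, it is up to two items, shown only to respondents who report an unplanned admission, and a form amendment. There may be a few more SAE reports to handle within the 15-day limit.
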